5.8.2 Emergency Room Visits or Outpatient Short Stays

All emergency room or short stays (<24 hours) visits related to heart failure will be documented and reported. Visit details must be reported to the Sponsor through the Hospitalization CRF and AE CRF through the electronic data capture system upon discovery of the event.

5.8.3 Hospitalizations

All hospitalizations with the associated reasons will be captured as sites become aware and will be reviewed during the follow-up visit. While hospitalized, the follow-up visit assessments will continue to be performed according to the follow-up schedule. Hospitalizations must be reported to the Sponsor through the EDC system upon discovery of the event or, at the latest, if the hospitalization is unknown to the implanting site (i.e. at another facility), during the next follow-up visit.

5.8.4 Right Heart Catheterization

CardioMEMS readings will be taken along with standard hemodynamic measurements collected any time a right heart catheterization (RHC) procedure is done as standard of care. See RHC data collection instruction on RHC CRF. Following sensor implant, subsequent RHC procedures or pulmonary artery catheter insertions must be performed under fluoroscopic guidance to avoid sensor dislodgement.

Resetting of the sensor baseline will be performed as deemed necessary by the investigator or the Sponsor. Baseline resetting may require an echocardiogram or a RHC procedure. Following the sensor implant, should a RHC procedure or PA catheter evaluation be clinically warranted, comparative pulmonary artery pressures utilizing the CardioMEMS HF System should also be obtained utilizing the hospital electronics unit.

5.8.5 Subject Home PA Pressure Readings

Following the sensor implant procedure, the Patient System Guide will be followed and subjects will be instructed on how to take their own pulmonary artery pressure measurements, utilizing the CardioMEMS HF System per standard of care. Patients can refer to the Patient System Guide for detailed information.

5.8.6 PA Pressure Readings in the Hospital

If a subject is hospitalized, seen in the emergency room (ER) or has a clinic visit, the CardioMEMS™ HF System may be used to obtain pulmonary artery pressure measurements at the investigator's discretion.

[figure not shown]
5.9 RAMP STUDIES

When any ramp studies are performed per institutional protocol, PA pressure data will also be collected with the CardioMEMS™ system with each change in pump speed.

5.10 STUDY FLOW CHART

A Study Flow Chart (Figure 1) and list of tests performed and assessments at each follow-up visit (Table 2) summarizes the requirements of this clinical investigation.

Figure 1 – Study Flow Chart

This confidential document is the property of Abbott and shall not be reproduced, distributed, disclosed or used without the express written consent of Abbott.

Table 2 – List of All Clinical Investigation Specific Tests and Procedures

Study Activity	Visit				
	Enrollment & Baseline + 3 days	1 Month (30 ±7 days window)	3 Month (90 ±7 days window)	6 Month (180 ±30 days window)	As occurs
Informed Consent Process, cardiovascular history and inclusion review	X				
Demographics	X				
Heart failure exam including vital signs	X	X	X	X	
Medical history	X				
Review cardiovascular medications, including dosages	X	X	X	X	X
LVAD pump parameters	X	X	X	X	X
CardioMEMS and LVAD device information	X				
CardioMEMS reading pre and post six minute walk test	X*	X	X	X	
EQ-5D-5L	X	X	X	X	
NYHA Class	X	X	X	X	
6 minute walk test	X	X	X	X	
Changes in CV medications					(X)
Adverse event, hospitalization and device malfunction					(X)
Deviation or withdrawal					(X)
CardioMEMS measurements during RHC					(X)
CardioMEMS measurements during RAMP testing					(X)

(as indicated)

* For Group A Only

Note: Medications logs and pump changes are to be updated when changes occur

This confidential document is the property of Abbott and shall not be reproduced, distributed, disclosed or used without the express written consent of Abbott.

5.11 DESCRIPTION OF ACTIVITIES PERFORMED BY SPONSOR REPRESENTATIVES

Trained Sponsor personnel may provide technical expertise and technical guidance on the use of the CardioMEMS™ HF System and HeartMate™ LVAS, including study training, technical training and will be available to respond to queries.

While Sponsor representatives may assist with these activities, the Principal Investigator remains responsible for ensuring all clinical investigation data is collected as required per CIP.

5.12 SUBJECT STUDY COMPLETION

Subject participation in the clinical investigation will conclude upon completion of the 6-month visit.

5.13 SUBJECT WITHDRAWAL

Subjects must be informed about their right to withdraw from the clinical investigation at any time and for any reason without sanction, penalty or loss of benefits to which the subject is otherwise entitled. Withdrawal from the clinical investigation will not jeopardize their future medical care or relationship with the investigator. Subjects will be requested to specify the reason for the request to withdraw. The investigator must make all reasonable efforts to retain the subject in the clinical investigation until completion of the clinical investigation.

If a subject at any time prior to the six month visit, has either the CardioMEMS™ or HeartMate™ device explanted, once the AE is captured, the patient should be withdrawn since they can no longer contribute meaningful study data. The reason for explant will be documented.

A subject will be considered 'Lost to Follow-up' after two missed visits and a minimum of two unsuccessful phone calls from investigational site personnel to the subject or contact to schedule the next follow-up visit. These two phone calls must be documented in the subject's hospital records. If the subject is deemed lost to follow-up a letter should be sent to the subject's last known address or to the subject's general practitioner (GP) and a copy of the letter must be maintained in the subject's hospital records.

When subject withdrawal from the clinical investigation is due to an adverse event, the subject will be followed until resolution of that adverse event or determination that the subject's condition is stable. The status of the subject's condition should be documented at the time of withdrawal.

In case of subject withdrawal, the site should make attempts to schedule the subject for a final study visit. At this final study visit, the subject will undergo assessments scheduled for the follow up visit subject is closest to.

5.14 STUDY COMMITTEES**5.14.1 Steering Committee (SC)**

A Steering Committee has been formed and has advised the Sponsor on key aspects related to the development, execution, analysis and reporting, and overall conduct of the clinical investigation.

5.14.2 Publication Committee (PC)

A Publication Committee shall be established to oversee study publications. Publication Committee membership may include members of the Steering Committee, a representative of Abbott and a statistician. The Publication Committee will be responsible for identifying, selecting and approving publication proposals and determining authorship according to a Publication Plan.

A Publication Committee charter will define membership of the committee and outline the roles and responsibilities of the committee, as well as rules to define authorship.

6 DATA ANALYSIS CONSIDERATIONS

This is a feasibility study evaluating commercially approved devices and has only descriptive endpoints. These endpoints will be evaluated via descriptive summary statistics without formal tests of hypothesis. The goal of this study is to gather data from subjects with both the CardioMEMS™ HF System and an FDA-approved HeartMate II™ (and HeartMate 3™ upon FDA approval) Left Ventricular Assist Device (LVAD). Both devices are commercially approved and will be used, as indicated, per the labeling. The underlying belief is that maintaining pulmonary artery pressure within a target range using CardioMEMS hemodynamic monitoring will improve outcomes in HeartMate LVAD patients.

Statistical analyses will be conducted to understand the role of hemodynamic monitoring in LVAD patients in order to:

- Characterize PA pressure measurements with the CardioMEMS HF System in LVAD patients under different clinical and physiologic conditions

To characterize PA pressure in LVAD patients, descriptive statistics will be used to quantify pressure at baseline, throughout the study and at 6 months using available data throughout the study. Raw PA pressures will be analyzed similarly at 1, 3, and 6 months. To characterize the impact of physical activity on PA pressure, descriptive statistics will be used to quantify the change in PA pressure before and after the 6MHW test.

- Characterize the effects of PA pressure on functional status, quality of life, and hospital readmissions of LVAD patients

To characterize the effects of PA pressure on clinical outcomes, patients will also be divided into subgroups based on time spent in the target PA pressure range and overall change in PA pressure during the follow-up period. Hospital readmissions and changes in functional status and quality of life will be quantified in these subgroups. The results can be used to find potential pressure ranges that are achievable in LVAD patients and have good clinical outcomes.

- Evaluate target ranges for PA pressure and assess the impact of medication and pump speed changes on PA pressures

The percentage of days that PA pressure is in the target range at different points in the study will be used to assess the impact of medication and pump speed changes on PA pressures.

The results of this study will be used to design future clinical trials. Any statistical significance levels (p-values) obtained from the statistical tests will be used to help identify endpoints that are sensitive to the potential benefits achieved from utilizing the CardioMEMS HF System to monitor and treat LVAD patients. Note that Group A and B patients will be analyzed together as one group and also as separate groups.

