4 CLINICAL INVESTIGATION DESIGN

4.1 CLINICAL INVESTIGATION DESIGN

The INTELLECT 2-HF Study is a prospective, non-randomized multicenter, single-arm observational study, which will be conducted at up to 25 U.S. centers, and will enroll up to 100 subjects.

The expected duration of enrollment is approximately 18 months with a six month follow-up period. Patients will exit the study when they complete their six month follow-up visit. The total duration of the clinical investigation is expected to be approximately two years.

Patients will be managed with the goal of achieving a PA diastolic pressure in a target range between 8 and 15 mmHg. Clinician discretion is allowed on how to reach this target range by remotely adjusting diuretic/ vasodilator therapy, or by changing pump speeds at clinic visits. The change implemented, and reason for the change, must be documented in the CRF. If no change is made when the patient is outside the target range, the clinician must document the clinical rationale for not making a change. It is recommended that adjustments to diuretic medications be the first approach unless an alternate approach is clinically more appropriate. Pump speed changes in these patients are expected to be infrequent.

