4.3.1 Descriptive Endpoints

1. Change in Six Minute Hall Walk (6MHW) distance from enrollment to six months
2. Changes in CardioMEMS PA pressure over time
3. Percentage of days PA pressure is in the pre-specified target range
4. Changes in PA pressure before 6MHW test to after 6MHW test
5. Device malfunction (e.g. loss of performance in either device)
6. NYHA classification at baseline and each scheduled follow-up visit
7. Health related quality of life (EQ-5D-5L)
8. All-cause hospitalization rate
9. Heart failure hospitalization rate including emergency department visits, or unscheduled clinic visits for worsening HF, volume management, and/or cardiovascular medication management
10. Change in 6MHWD, NYHA class, health related quality of life, or unscheduled hospitalizations by PA pressure

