6.1 ANALYSIS OF ENDPOINTS

6.1.1 Descriptive Endpoints

The following endpoints will be analyzed using descriptive statistics. Continuous variables will be summarized using numbers of subjects, mean, standard deviation, median, minimum, and maximum. Categorical variables will be summarized using frequency and percentages. Rate data will be summarized using events per patient-time.

1. Change in Six Minute Hall Walk (6MHW) distance will be summarized as change from baseline and using raw values, at 1, 3, and 6 months.
2. Changes in CardioMEMS™ PA pressure over time will include PA systolic, diastolic and mean pressures; heart rate; and cardiac output (calculated using latest algorithm for CardioMEMS) and will be summarized at baseline, throughout the study, and at 6 months.
3. Percentage of days over 6 months that PA diastolic pressure is between 8 and 15 mmHg will be summarized using the total number of days that pressures were measured as the denominator. The percentage will also be calculated at different points during the study. This endpoint will be used to assess the impact of medication and pump speed changes on PA pressures.
4. Changes in PA pressure before the 6MHW test to after the 6MHW test will be summarized at baseline (Group A only) and at 1, 3, and 6 months for both groups.
5. Device malfunction will include all instances of loss of performance of either device and will be summarized separately by device and type of loss of performance at 1, 3, and 6 months.
6. NYHA classification will be analyzed as a categorical variable and as a continuous variable at baseline, 1, 3, and 6 months. Change from baseline in NYHA will be analyzed similarly.
7. Health related quality of life (EQ-5D-5L) total score and visual analogue scale will be scored using the recommended scoring algorithms and analyzed at baseline, 1, 3, and 6 months. The change from baseline in EQ5D-5L will be analyzed similarly.
8. All-cause hospitalization rate will be summarized over 6 months in units of events per patient-time.
9. Heart failure hospitalization rate including emergency department visits, or unscheduled clinic visits for worsening HF, volume management, and/or cardiovascular medication management will be summarized over 6 months in units of events per patient-time.
10. Change in 6MHWD, NYHA class, EQ-5D-5L, or unscheduled hospitalizations will be analyzed descriptively according to subgroups based on PA diastolic pressure.

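### PA pressure is related to outcomes only through subgroups; adding an analysis that keeps each exposure continuous would recover precision at almost no cost

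*Combined protocol and SAP*

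**What the plan says.** Section 6 lists three objectives. Under the second it states that "patients will also be divided into subgroups based on time spent in the target PA pressure range and overall change in PA pressure", and that "Hospital readmissions and changes in functional status and quality of life will be quantified in these subgroups". The stated use is that "The results can be used to find potential pressure ranges that are achievable in LVAD patients and have good clinical outcomes".

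The matching endpoint is number 10. Section 4.3.1 lists it as "Change in 6MHWD, NYHA class, health related quality of life, or unscheduled hospitalizations by PA pressure". Section 6.1.1 says these outcomes "will be analyzed descriptively according to subgroups based on PA diastolic pressure". Time in range is not named in either version of endpoint 10; it appears as a grouping variable only in section 6, beside overall change in pressure.

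Endpoint 3 in section 6.1.1 defines a continuous quantity for each patient: "Percentage of days over 6 months that PA diastolic pressure is between 8 and 15 mmHg will be summarized". It is summarised on its own and is not linked to any outcome.

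On size, section 4.1 says the study "will enroll up to 100 subjects", and section 6 adds that "Group A and B patients will be analyzed together as one group and also as separate groups". Section 6 describes the endpoints as descriptive and without formal hypothesis tests, but allows p-values to help pick out sensitive endpoints for later trials. The number of subgroups, the cut points and the expected distribution of any exposure are not given.

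**The concern.** Cutting a continuous exposure treats patients just either side of a cut as different, and patients at the two ends of one subgroup as the same. If outcome changes steadily with exposure, the within-subgroup variation in exposure is thrown away and the association is estimated less precisely.

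That matters here because relating pressure to outcome is one of only three objectives, and its results are meant to shape later trials. A table of outcome means by undefined subgroup also gives no quantity per unit of exposure, such as metres walked per 10 percentage points of days in range, which is what someone planning a later trial would look for. Analysing Groups A and B separately thins the subgroups further.

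**Working it through.** **Nothing to reproduce.** Section 6.2 gives 100 subjects with no effect size, standard deviation, power or precision behind it. The calculation below therefore measures only what grouping costs relative to the same data left uncut.

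**Inputs.** N = 100 (section 4.1, an upper limit). Exposure distribution and cut points: not in the documents, so a range is shown.

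**Formula.** For a linear relation, the share of information kept is the between-group variance of the exposure divided by its total variance. The loss is 1 minus that share.

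- Median split, normal exposure: kept = 2/π = 0.637, loss 36.3%.
- k equal groups, uniform exposure: kept = 1 − 1/k². For k = 2, 3 and 4 this is 0.750, 0.889 and 0.938, so the loss is 25.0%, 11.1% and 6.2%.
- 80/20 split, uniform on 0–1: group means 0.4 and 0.9; kept = 0.8 × 0.2 × 0.5² ÷ (1/12) = 0.04 ÷ 0.0833 = 0.48, loss 52.0%.
- 80/20 split, Beta(1,2), with the top 20% cut off in the long tail: group means 0.241 and 0.702, variance 1/18; kept = 0.16 × 0.461² ÷ 0.0556 = 0.61, loss 39%.

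| Split | Uniform | Beta(2,2) | Normal |
|---|---|---|---|
| Two equal groups | 25.0% | 29.7% | 36.3% |
| Tertiles | 11.1% | 14.5% | 20.7% |
| Quartiles | 6.2% | 8.7% | 13.9% |
| 80/20 | 52.0% | 50.6% | 51.0% |

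These are not bounds. A U-shaped Beta(0.5,0.5) loses 19% at the median, and at 80/20 a Beta(1,3) loses 35% and a Beta(5,2) loses 62%.

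**As precision.** For a weak association the confidence interval widens by about 1/√(share kept):

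- Median split: 1/√0.750 = 1.15 to 1/√0.637 = 1.25.
- Tertiles: 1/√0.889 = 1.06 to 1/√0.793 = 1.12.
- Quartiles: 1/√0.938 = 1.03 to 1/√0.861 = 1.08.
- 80/20: 1/√0.61 = 1.28 to 1/√0.48 = 1.44.

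Equivalently, 100 patients carry the linear information of about 64–75 after a median split, 79–89 after tertiles and 86–94 after quartiles.

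**As power, for scale only.** At two-sided 5% (an assumption), a correlation of 0.277 has 80% power with 100 patients uncut. After a median split it has about 60% (normal) to 67% (uniform), and after normal tertiles about 70%.

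**If the relation is curved.** Simulated power with 100 patients, a normal exposure and 9% of outcome variance explained:

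| True shape | Straight line | Tertiles (F test) | Flexible continuous term |
|---|---|---|---|
| Linear | 86% | about 68% | 79% |
| Symmetric U | 9% | 23% | 75% |

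For a step at the median, a median split has about 80% and a straight line 68% (75% with a uniform exposure). A symmetric curvature term picks up nothing of such a step, so it only spends a degree of freedom there.

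**The case against.** **The relation may not be linear.** This is the strongest objection. The target range has a lower as well as an upper limit. Section 2 mentions avoiding hypovolemia, and Appendix F treats pressures on both sides of the range as needing attention. For PA diastolic pressure, the exposure in item 10, a non-monotone relation is plausible, and the stated purpose is to find useful ranges. This stands against replacing the subgroups with a single slope, which misses a U-shape almost entirely. It does not stand against a continuous term that allows curvature: that does better than tertiles in both the linear and the U-shaped case.

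**The study is descriptive.** It sets no hypothesis and no success criterion, so there is no planned power to lose. That is correct, and the power figures above only illustrate precision. But a fitted curve with a confidence interval is also descriptive and needs no test.

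**The wording leaves room for other analyses**, since patients will *also* be divided into subgroups. True, but none relating pressure to outcome is described.

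**Unfixed cut points are a separate matter.** They are a pre-specification gap that would remain even if grouping were accepted. They matter here only because they prevent the loss from being narrowed to one figure.

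**Conclusion.** The point holds as a matter of precision and is worth acting on. Subgrouping is the only route the plan describes from pressure to outcome, and no continuous analysis is planned. The loss ranges from 6–14% of the linear information with quartiles to 25–36% with a median split and 39–52% with an 80/20 split. This rests on a roughly linear relation and on assumed exposure distributions.

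Four stronger readings are tempting, and the documents do not support them:

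- *Grouping discards a fixed quarter to a third of the information.* That range fits only two groups cut near the median; the plan gives neither the number of groups nor the cuts.
- *Endpoint 10 cuts the percentage of days in range.* Endpoint 10 names PA diastolic pressure. Time in range is a grouping variable only in section 6, together with overall change in pressure, so a remedy built on time in range alone would leave out two of the three named exposures.
- *The study loses stated power.* None is stated.
- *The subgroup tables are wrong.* They are a reasonable display and can show a step that a smooth curve would blur.

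**What to change.** In section 6 (second objective) and item 10 of section 6.1.1, keep the subgroup tables. Add, for each exposure the plan already names (percentage of days in range, overall change in PA pressure, PA diastolic pressure), a model with that exposure uncut and curvature allowed through a restricted cubic spline or a quadratic term:

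- change in 6MHWD and EQ-5D-5L: linear regression;
- NYHA class: ordinal regression;
- hospitalizations: Poisson or negative binomial regression with log patient-time as offset.

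Show each fitted curve with its 95% CI. Where the relation is about linear, also give a per-unit estimate, for example per 10 percentage points of days in range. Describe all results as associations.

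The cost is a few sentences and some extra model runs on data already collected, with no new patients, visits or measurements. The flexible term spends one or two degrees of freedom and can do worse than grouping if the true relation is a sharp step; the retained tables would show that.

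### Time-in-range subgroups and readmissions share the same six months, so an admission can help set its own subgroup: word the tables as associations, state the windows, and add one supportive table without post-admission readings

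*Combined protocol and SAP*

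**What the plan says.** Section 6 introduces the analysis with "To characterize the effects of PA pressure on clinical outcomes". Patients are to be "divided into subgroups based on time spent in the target PA pressure range and overall change in PA pressure during the follow-up period", after which "Hospital readmissions and changes in functional status and quality of life will be quantified in these subgroups". The stated use is that "The results can be used to find potential pressure ranges that are achievable in LVAD patients and have good clinical outcomes". The study objectives in Section 4.2 also speak of effects of PA pressure.

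Section 6.1.1 supplies the measures:

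- Item 3 takes the percentage of days over six months with PA diastolic pressure between 8 and 15 mmHg, "using the total number of days that pressures were measured as the denominator". It adds that "The percentage will also be calculated at different points during the study", but does not tie those points to the subgroups.
- Item 8 states that "All-cause hospitalization rate will be summarized over 6 months in units of events per patient-time".
- Item 10 says that unscheduled hospitalizations, with the other outcomes, "will be analyzed descriptively according to subgroups based on PA diastolic pressure". It gives no window and no cut-point.

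Readings after an admission will be among the data. Patients take readings at home (Section 5.8.5, no frequency stated). In-hospital readings are at the investigator's discretion (Section 5.8.6). Scheduled visit assessments, which include PA readings (Section 5.5.2), continue if a visit falls during a stay (Section 5.8.3). Under Section 5.6, treatment steers PA diastolic pressure toward 8 to 15 mmHg throughout follow-up.

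**The concern.** The grouping variable is built from the whole follow-up and the outcome is counted over that same follow-up. If pressure is disturbed after an admission, or is brought into range by the treatment given for it, those days enter the patient's time in range and can move the patient across the subgroup boundary. The admission then helps decide the column in which it is counted.

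If admissions push pressure out of range, the subgroup with little time in range appears to have more readmissions even when pressure has no influence on them. If treatment around the admission brings pressure into range, the false link runs the other way.

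At stake is the one use the plan gives these tables: finding pressure ranges that go with good outcomes, to inform later trials. From the planned table alone, a reader cannot tell how much of a difference comes from readings taken after admissions.

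**Working it through.** **The plan's own figures.** The plan gives no subgroup effect, cut-point or precision target, and Section 6.2 states 100 subjects without a derivation, so there is nothing to reproduce. From the documents I use 100 subjects, six months, and two readmission figures in Section 2: about 80% readmitted within a year of implant, and 10% of readmissions due to pressure/volume management or worsening HF. Every other input below is an assumption.

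**How much follow-up comes after an admission.** With a constant hazard, rate = −ln(1 − 0.80) = 1.61 per patient-year.

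- Expected admissions: 100 × 1.61 × 180/365 ≈ 79, about 80.
- Patients admitted within six months: 1 − exp(−1.61 × 0.5) = 55%.
- Patient-days after a first admission: 1 − 0.553/0.805 = 31%.
- With one-year risks of 60% to 70% instead, 37% to 45% of patients are admitted and 20% to 25% of patient-days follow a first admission.
- At the 10% share, about 8 admissions are of the pressure/volume or HF kind.

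**Sampling error.** For two equal groups sharing E events, the 95% factor on a rate ratio is exp(1.96 × √(4/E)). This is 1.55 for 80 events, 1.86 for 40 and 4.0 for 8.

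**Null simulation of the planned table.** Admissions are independent of underlying pressure, so the true ratio is 1.00. Assumptions: 100 patients, 180 days, mean 60% of days in range, between-patient SD 0.15 to 0.25, median split, and 7 to 30 days per disturbing admission forced out of range (outward) or into range (inward). The ratio is the all-cause admission rate, low over high time in range.

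| Share of admissions that disturb pressure | Outward | Inward |
|---|---|---|
| 10%, constant risk | 1.02–1.11 | 0.93–0.99 |
| 10%, frailty variance 0.5–1.0, rate rescaled to keep 80% readmitted | 1.02–1.32 | 0.82–0.99 |
| 100%, constant risk (worst case) | 1.15–2.48 | 0.55–0.93 |

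Forcing every disturbed day across the boundary is severe. With a 6 mmHg shift instead, the worst case is 0.72 to 1.63. With a 3 mmHg shift after every admission, decaying over 30 or 60 days, the planned table gives 1.13 to 1.33 for upward shifts and 0.82 to 0.93 for downward shifts.

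**Overall change.** The plan does not say which readings are subtracted from which. Under trial definitions (last 30 days, or all later days, minus the first 7), the ratio is 0.94 to 1.06 at the 10% share. Shifts of mixed direction give 0.99 to 1.01 even if every admission disturbs pressure. This shows a missing definition, not a bias.

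**The supportive table.** Leave out readings during each stay (assumed 5 days) and for 30 days after discharge, and count all admissions. For time in range, the null ratio returns to 0.97–1.03 when the disturbance lasts up to 30 days. Its limits:

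- If the disturbance lasts 45 or 60 days, the worst case still shows 1.21–1.37 or 1.58–1.95 (1.03–1.04 or 1.05–1.08 at the 10% share).
- A true link (threefold hazard while out of range) falls from 1.28–1.67 in the planned table to 1.19–1.49.
- With no disturbance at all, a steep fall in pressure over follow-up and admission risk that varies between patients, it shows 1.06–1.14 where the planned table shows 0.96–1.01.

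**The case against.** The strongest reply is that this is a descriptive feasibility study with no success criteria and no formal tests. At the only share the documents give, the all-cause distortion is small beside sampling error. The 80% figure is also for the first year after implant, while these subjects have had at least three months of LVAD support, so their risk may differ. All of that stands, and it is why the point is optional. It does not answer the wording, since the plan speaks of effects and names a use for the tables.

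A second reply is that the supportive table makes the pressure window depend on the outcome. That is also right. The table can create a modest false link of its own, so it belongs beside the planned table and not in its place.

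Four stronger readings are tempting, and the documents do not support them:

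- *A tested conclusion is invalid.* Section 6 mentions p-values as a help in identifying sensitive endpoints, but nowhere says that this subgroup contrast is tested.
- *In-hospital readings drive the result.* They are discretionary, or arise only when a scheduled visit falls in a stay. The mechanism rests mainly on home readings after discharge.
- *The overall-change subgroups are biased.* They are undefined, and no material distortion is shown at the documented 10% share.
- *Item 10 makes a causal claim.* It does not. The effects wording is in Sections 4.2 and 6.

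**Conclusion.** The overlap is in the text, and confidence in it is high: time in range and readmissions cover the same six months, with no order in time and no rule for readings after an admission. The planned table supports a statement of association and cannot, on its own, identify pressure ranges with good outcomes.

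Confidence in the size is low. With constant risk, the all-cause distortion is slight if about 10% of admissions disturb pressure. It becomes large only if most do. Strong variation in risk between patients widens even the 10% case (0.82 to 1.32 in the severe model). The direction is not known in advance. These figures rest on assumed pressure distributions, disturbance lengths and daily readings; only the 80% and 10% come from the documents. Severity: optional.

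**What to change.** (a) In Section 4.2 and in Section 6 (second objective), replace 'effects of PA pressure on' with 'associations of PA pressure with'. Item 10 needs no such edit.

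(b) State the pressure window (for example, all measured days from enrollment, or from the first post-implant reading in Group B, to Month 6), the outcome window, and how overall change is calculated.

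(c) Keep the planned tables as the main ones and add: *As a supportive analysis, the time-in-range readmission table will be repeated with patients reclassified after leaving out PA readings during each admission and for 30 days after discharge. All admissions remain counted.* State beside it that a difference between the two tables signals sensitivity to post-admission readings, that neither is an unbiased estimate, and that the added table has the limits shown above and does not remove pressure changes that begin before admission.

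(d) Optional: a Month 3 landmark table that classifies patients up to Month 3 and counts admissions afterwards. It halves the events (×/÷1.86 against ×/÷1.55) and should not replace the planned comparison.

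Cost: a few lines of text and a little programming, with no new data or visits. With daily readings and about 80 admissions, the exclusion drops about 13% of patient-days. The ceiling before overlap and end of follow-up is 80 × 35 / 18,000 = 16%. At 197 admissions, the expected count with frailty variance 1.0, it drops about 25%. Cutting all readings at the first admission is not a good substitute: with pressures falling 4 mmHg over follow-up, it gave 1.25 to 1.37 under the null.
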